4.1.2 ITT Population

The ITT population is defined as all randomized patients, irrespective of whether or not the patient received the assigned treatment. Patients will be grouped according to the treatment assigned at randomization. The ITT Population will be used for efficacy sensitivity analysis.

4.1.3 IA Treated Patients Population

The IA Treated Patients Population is defined as all patients randomized at least 5 months prior to the interim analysis CCOD that have received at least any dose of study treatment. Analysis by treatment arm performed on the IA Treated Patients Population will be grouped according to the actual treatment received. The IA Treated Patients Population will be used at interim analysis for the efficacy analysis.

4.1.4 Crossover Population

The Crossover Patients, Treated Patients Population or Safety Population is defined as all patients randomized to the atezolizumab monotherapy arm that crossed-over to the tiragolumab in combination with atezolizumab arm, and received at least any dose of tiragolumab after cross-over but not prior to cross-over.

4.1.5 Pharmacokinetic-Evaluable Population

The Pharmacokinetic-Evaluable Population is defined as all patients who received any dose of study treatment and who have at least one post-baseline PK sample available.

4.1.6 Safety Population

The safety population is defined as patients who received at least one dose of tiragolumab or atezolizumab. The Safety Population is identical to the Treated Patients Population (see Section 4.1.1) and will be used for the safety analysis.

4.2 ANALYSIS OF STUDY CONDUCT

Enrollment, major protocol deviations including major deviations of inclusion/exclusion criteria, and reasons for discontinuation from the study will be summarized by treatment arm for the ITT Population. Study treatment administration and reasons for discontinuation from study treatment will be summarized for the Safety Population.

4.3 ANALYSIS OF TREATMENT GROUP COMPARABILITY

Demographic characteristics (age, race/ethnicity, geographic region), baseline disease characteristics (histology, initial diagnosis stage, target lesions size, disease location, PD-L1 expression, number of prior lines of systemic anti-cancer therapy, prior bevacizumab use) and stratification factors (ECOG performance status, prior use of (chemo) radiotherapy, treatment history) will be summarized by treatment arm for the Treated Patients Population and for the IA Treated Patients Population at interim analysis.

Baseline values are the last available data obtained prior to the patient receiving the first dose of any component of study treatment on Cycle 1, Day 1 (or at screening, for patients who were not treated), unless otherwise noted. Descriptive statistics (mean, median, standard deviation, minimum, maximum) will be presented for continuous variables, and frequencies and percentages will be presented for categorical variables.

4.4 EFFICACY ANALYSIS

4.4.1 Primary Efficacy Endpoint

4.4.1.1 Objective Response Rate (confirmation required)

The primary efficacy endpoint is confirmed objective response rate (ORR), defined as the proportion of patients with a confirmed objective response, either complete response (CR) or partial response (PR), observed on two consecutive assessments \geq 4 weeks apart with the use of RECIST v1.1, based on IRC assessment.

In the primary efficacy analysis, patients without any post-baseline tumor assessments will be considered non-responders. Confirmed ORR will be analyzed for the Treated Patients Population at primary analysis. Confirmed ORR will be analyzed for the IA Treated Patients Population at interim analysis.

A one-sample z-test for proportion will be used to compare the confirmed ORR of the tiragolumab in combination with atezolizumab arm to the historical reference (see Section 2.2.2). No formal treatment comparison will be performed between the two arms or between the atezolizumab monotherapy arm and the historical reference.

An estimate of the confirmed ORR and its 95% CI will be calculated for each treatment arm using the Clopper-Pearson method.

In order to characterize responders, descriptive statistics (e.g. median, range) will be provided for time from randomization to response (TTR) for patients with an objective response.

4.4.2 Secondary Efficacy Endpoint

4.4.2.1 Duration of Response

A secondary endpoint is duration of response (DOR), defined for patients with a confirmed objective response, as the time from the first documented objective response to documented disease progression with the use of RECIST v1.1, as determined by the IRC, or death from any cause, whichever occurs first.

Data for patients who are alive and who have not experienced disease progression at the time of analysis will be censored at the date of the last tumor assessment at which they were known to be progression-free. DOR will be analyzed in a subset of patients (those who achieve an objective response) from the Treated Patients Population at primary analysis and from the IA Treated Patients Population at interim analysis.

The analysis of DOR is based on a non-randomized subset of patients (those who achieve an objective response); therefore, comparisons between treatment arms will be made for descriptive purposes only. In particular, Kaplan-Meier methodology will be used to estimate the median DOR for each treatment arm, and Kaplan-Meier curves will be produced. The Brookmeyer-Crowley methodology will be used to construct the 95% CI for the median DOR for each treatment arm (Brookmeyer and Crowley 1982). The Kaplan-Meier approach will also be used to estimate 6-month DOR rate in each arm.

4.4.2.2 Disease Control Rate

A secondary endpoint is

The methodologies described for the analysis of confirmed ORR will be used for the analysis of DCR (except the formal treatment comparison with the historical reference that will not be performed on DCR).

4.4.2.3 Best Clinical Response

A secondary endpoint is best clinical response (BCR), defined as the proportion of patients with a CR, PR, or SD, as clinically determined by the investigator.

The methodologies described for the analysis of confirmed ORR will be used for the analysis of BCR (except the formal treatment comparison with the historical reference that will not be performed on BCR). DOR as clinically determined by the investigator will also be provided, and the methodology will be the same as used for the analysis of the IRC DOR.

4.4.2.4 Progression-Free Survival

A secondary efficacy endpoint is progression-free survival (PFS), defined as the time from randomization to the first documented disease progression as determined by the IRC with the use of RECIST v1.1, or death from any cause, whichever occurs first.

Data for patients who are alive and have not experienced disease progression at the time of analysis will be censored at the date of the last tumor assessment at which they were known to be progression-free with radiographic evidence. Data for patients with no post-baseline tumor assessment will be censored at the date of randomization. PFS will be analyzed in the Treated Patients Population and in the IA Treated Patients Population at interim analysis

Kaplan-Meier methodology will be used to construct survival curves for each treatment arm and to estimate median PFS for each treatment arm. The Brookmeyer-Crowley methodology will be used to construct the 95% CI for the median PFS for each treatment arm (Brookmeyer and Crowley 1982).

The Kaplan-Meier approach will also be used to estimate 6-month PFS rate in each arm.

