2. STUDY DESIGN

Study WO42017 is a randomized, Phase II, global, multicenter, open-label study designed to evaluate the efficacy and safety of tiragolumab plus atezolizumab and atezolizumab monotherapy in patients with metastatic and/or recurrent PD-L1-positive cervical cancer after progression or recurrence from at least one platinum-based but no more than two prior systemic therapies.

Approximately 160 patients will be randomized in this study global enrollment phase in a 3:1 ratio. Additional patients may be subsequently randomized in a

. Women with Eastern Cooperative Oncology Group (ECOG) Performance Status of 0 or 1 who have metastatic and/or recurrent PD-L1–positive cervical cancer are eligible (refer to protocol synopsis in Appendix 1 for complete eligibility criterion).

In the doublet arm, patients will receive atezolizumab at a fixed dose of 1200 mg administered by IV infusion Q3W on Day 1 of each 21-day cycle, followed by tiragolumab at a fixed dose of 600 mg administered by IV infusion Q3W also on Day 1 of each 21-day cycle.

In the atezolizumab monotherapy arm, patients will receive atezolizumab at a fixed dose of 1200 mg administered by IV infusion Q3W on Day 1 of each 21-day cycle.

Treatment may be continued as long as patients are experiencing clinical benefit, as assessed by the investigator, in the absence of unacceptable toxicity or symptomatic deterioration attributed to disease progression after an integrated assessment of radiographic data, biopsy results (if available), and clinical status. Patients who meet the criteria for equivocal disease progression per RECIST v1.1 will be permitted to continue treatment (tiragolumab in combination with atezolizumab or atezolizumab alone) if they meet all of the following criteria:

- Evidence of clinical benefit, as assessed by the investigator
- Absence of symptoms and signs (including worsening of laboratory values indicating unequivocal progression of disease)
- No decline in ECOG Performance Status that can be attributed to disease progression

[figure not shown]
 Absence of tumor progression at critical anatomical sites (e.g., leptomeningeal disease) that cannot be managed by protocol-allowed medical interventions

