2.2.1 Type I Error Control
Type I error for the study is (one-sided).
The primary endpoint is confirmed ORR, defined as the proportion of patients with a complete response (CR) or a partial response (PR) on two consecutive occasions ≥4 weeks apart, as determined by an independent review committee (IRC) according to RECIST v1.1.
Primary statistical test is a significance level, and the ORR of the doublet arm will be compared to a historical reference of 14.6% (Chung et al. 2019). This is the only comparison with a statistical hypothesis testing.
No type I error control is applied for descriptive comparisons, including that of the atezolizumab monotherapy ORR to the historical reference.

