4.4.2.5 Overall Survival

A secondary efficacy endpoint is overall survival (OS). OS is defined as the time from randomization to death from any cause.

Data for patients who are not reported as having died at the time of analysis will be censored at the date last known to be alive. Data for patients who do not have post-baseline information will be censored at the date of randomization. OS will be analyzed for the Treated Patients Population and in the IA Treated Patients Population at interim analysis.

Kaplan-Meier methodology will be used to construct survival curves for each treatment arm and to estimate median OS for each treatment arm. The Brookmeyer-Crowley

methodology will be used to construct the 95% CI for the median OS for each treatment arm (Brookmeyer and Crowley 1982).

The Kaplan-Meier approach will also be used to estimate 6-month OS rate in each arm, along with 95% CI calculated using Greenwood's formula. 12-month OS rate in each arm will also be provided as appropriate.

Duration of survival follow-up will be summarized for all patients in the analysis using descriptive statistics (median, range). Duration of survival follow-up is defined as the survival time for all patients in the analysis (whether a patient is alive or has died).

4.4.3 Disease Control Rate Disease control rate is defined as the proportion of patients with either confirmed objective response (CR or PR observed on The methodologies described for the analysis of confirmed ORR will be used for the analysis of DCR (except the formal treatment comparison with the historical reference that will not be performed on DCR

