Appendix 1 Protocol Synopsis

PROTOCOL SYNOPSIS

TITLE: A PHASE II, SAFETY, AND EFFICACY STUDY OF

TIRAGOLUMAB PLUS ATEZOLIZUMAB AND ATEZOLIZUMAB MONOTHERAPY IN PATIENTS WITH METASTATIC AND/OR

RECURRENT PD-L1-POSITIVE CERVICAL CANCER

PROTOCOL NUMBER: WO42017

VERSION NUMBER: 4

EUDRACT NUMBER: 2019-004895-21

IND NUMBER: 147026

NCT NUMBER: NCT04300647

TEST PRODUCTS: Atezolizumab (RO5541267)

Tiragolumab (RO7092284)

PHASE: Phase II

INDICATION: Cervical cancer

SPONSOR: F. Hoffmann-La Roche Ltd

Objectives and Endpoints

Efficacy Objectives

Primary Efficacy Objective

The primary efficacy objective for this study is to evaluate the efficacy of tiragolumab in combination with atezolizumab and of atezolizumab monotherapy on the basis of the following endpoint:

 Objective response rate (ORR), defined as the proportion of patients with a complete response (CR) or a partial response (PR) on two consecutive occasions ≥4 weeks apart, as determined by an independent review committee (IRC) according to Response Evaluation Criteria in Solid Tumors, Version 1.1 (RECIST v1.1)

Secondary Efficacy Objective

The secondary efficacy objective for this study is to evaluate the efficacy of tiragolumab in combination with atezolizumab and of atezolizumab on the basis of the following endpoints:

- Duration of response (DOR), defined as the time from the first occurrence of a documented objective response to disease progression or death from any cause (whichever occurs first), as determined by the IRC according to RECIST v1.1
- Disease control rate (DCR), defined as the proportion of patients with a CR, PR, or stable disease (SD), as determined by an IRC according to RECIST v1.1
- Best clinical response rate (BCR), defined as the proportion of patients with a CR, PR, or SD, and the DOR as clinically determined by the investigator

- Progression-free survival (PFS) after randomization, defined as the time from randomization to the first occurrence of disease progression, as determined by the IRC according to RECIST v1.1, or death from any cause, whichever occurs first
- PFS rate at 6 months, defined as the proportion of patients who have not experienced disease progression, as determined by the IRC according to RECIST v1.1, or death from any cause at 6 months post-randomization
- Overall survival (OS) after randomization, defined as the time from randomization to death from any cause

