Patients will undergo tumor assessments at baseline and every 6 weeks $(\pm 7 \text{ days})$ for 48 weeks following Day 1 of Cycle 1 regardless of treatment delays. After the completion of the Week 48 tumor assessment, tumor assessments will be required every 9 weeks $(\pm 7 \text{ days})$ regardless of treatment delays until unequivocal radiographic disease progression per RECIST v1.1 (or loss of clinical benefit for patients who continue study treatment after disease progression per RECIST v1.1), withdrawal of consent, death, or study termination by the Sponsor, whichever occurs first. Patients who are treated beyond disease progression per RECIST v1.1 will undergo tumor assessments at the frequency described above until study

treatment is discontinued. Patients who discontinue treatment for reasons other than radiographic disease progression per RECIST v1.1 (e.g., toxicity, symptomatic deterioration) will continue scheduled tumor assessments at the frequency described above until radiographic disease progression per RECIST v1.1, withdrawal of consent, death, or study termination by the Sponsor, whichever occurs first. In the absence of radiographic disease progression per RECIST v1.1, tumor assessments should continue regardless of whether a patient starts a new anti-cancer therapy.

Response will be assessed according to RECIST v1.1. Objective response will be determined at a single timepoint by the IRC according to RECIST v1.1.

Crossover is allowed from the atezolizumab monotherapy arm to the tiragolumab plus atezolizumab arm after unequivocal progressive disease has been recorded during atezolizumab monotherapy, at the discretion of the investigator and after consultation with the Medical Monitor. For patients who crossover from atezolizumab monotherapy to tiragolumab plus atezolizumab, the tumor assessment just preceding crossover will serve as a rebaseline scan against which all subsequent scans will be compared.

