The Sponsor will monitor patient safety throughout the study. In addition to the ongoing assessment of the incidence, nature, and severity of adverse events; deaths; vital signs; and laboratory abnormalities, the Sponsor will review all cumulative data at regular intervals during the study.

Internal Monitoring Committee

An Internal Monitoring Committee (IMC) composed of representatives from safety science, clinical science, and statistics, who are independent from the study team, will be established. Representatives from other functions may be added on an ad hoc basis depending on the nature of the findings. The primary responsibility of the IMC is to evaluate the safety, not

efficacy, of treatment arms being evaluated. The IMC will share responsibility with the study team for the monitoring of patient safety.

The IMC may meet during the course of the study. The IMC may conduct an ad hoc meeting should an unexpected safety concern arise, as specified in the IMC Charter. At the time of each review of cumulative data, the IMC may make recommendations in consideration of the totality of the available data. Specific operational details such as the committee's composition, timing of meetings, and members' roles and responsibilities will be detailed in an IMC Charter.

Number of Patients

Approximately 160 patients with metastatic and/or recurrent PD-L1—positive cervical cancer will be enrolled in the global enrollment phase. A total of approximately

Target Population

Inclusion Criteria

Patients must meet the following criteria for study entry:

[figure not shown]
- Signed Informed Consent Form
- Age≥18 years at time of signing Informed Consent Form
- Life expectancy ≥ 12 weeks
- Ability to comply with the study protocol
- ECOG Performance Status of 0 or 1
- Histologically confirmed recurrent or persistent squamous cell carcinoma, adenosquamous carcinoma, or adenocarcinoma of the cervix (neuroendocrine, clear cell, and sarcoma histologies are not allowed) after progression on or after 1–2 lines of prior systemic chemotherapy in the metastatic/recurrent setting that is not amenable to curative treatment with systemic chemotherapy, surgery, and/or radiotherapy

At least one prior line of platinum-based systemic chemotherapy.

Radiosensitizing cisplatin given with radiotherapy is not considered a line of systemic chemotherapy.

- Measurable disease, defined as:

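### The PFS censoring rule for patients with no post-baseline scan omits the condition that the patient is alive, so a death before the first scan could be censored at day 0

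*SAP*

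**What the plan says.** SAP Section 4.4.2.4 defines PFS as the time from randomization to IRC-determined progression or death from any cause, whichever is earlier. Two censoring sentences follow.

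- The first is limited to living, progression-free patients: "Data for patients who are alive and have not experienced disease progression at the time of analysis will be censored", at the last scan that showed no progression.
- The second has no such limit: "Data for patients with no post-baseline tumor assessment will be censored at the date of randomization".

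The synopsis in Appendix 1 repeats the definition with death as an event. It lists among the secondary endpoints the "PFS rate at 6 months, defined as the proportion of patients who have not experienced disease progression", and goes on to include death from any cause. Section 4.7 (Missing Data) refers back to 4.4.2.4 and adds no rule. PFS is analyzed in treated patients, and the Kaplan-Meier summaries are the median and the 6-month rate per arm.

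**The concern.** A treated patient who dies before the first scan, due at about week 6, has an event under the definition. She also has no post-baseline tumor assessment, so under the second censoring sentence as written she is censored at day 0. The SAP does not say which rule takes precedence.

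If the sentence is programmed literally, these deaths leave the risk set at time 0 and the 6-month PFS rate comes out too high. The error is larger in the arm with the larger share of such deaths. The wording matters because Section 4 says that, for a regulatory filing, the SAP's analyses replace those in the protocol. In an open-label study, the event status of early deaths should not be left to a later choice.

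**Working it through.** **Step 1: the rules side by side, for a treated patient who dies at week 4 without a scan**

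| Rule | Condition | Result |
|---|---|---|
| PFS definition (4.4.2.4; Appendix 1) | progression or death, no scan required | event at week 4 |
| First censoring sentence (4.4.2.4) | alive and progression-free | does not apply |
| Second censoring sentence (4.4.2.4) | no post-baseline tumor assessment | censored at day 0 |

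The OS section (4.4.2.5) has a similar pair of sentences, the second being "Data for patients who do not have post-baseline information will be censored at the date of randomization". That one cannot collide with a death, because a recorded death is itself post-baseline information. It is not a tumor assessment, so the PFS sentence can collide.

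**Step 2: can such patients occur?** Appendix 1 states "Patients will undergo tumor assessments at baseline and every 6 weeks" (±7 days), so the unscanned period lasts about six weeks. Entry requires ECOG 0 or 1 and "Life expectancy ≥ 12 weeks". These criteria make a death in that period less likely but do not exclude it.

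**Step 3: size of the effect.** No figure in the SAP depends on this rule, so there is none to reproduce. Let q be the share of an arm that dies before any scan, and S_rest(6) the 6-month PFS of the others. The SAP gives neither, so both q and the true 6-month rate are assumed.

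- Deaths counted as events: S(6) = (1 − q) × S_rest(6)
- Deaths censored at day 0: S(6) = S_rest(6)
- Ratio, literal to definition: 1/(1 − q), provided no other patient progresses or is censored before those deaths

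| True 6-month rate | q = 1% | q = 3% | q = 5% |
|---|---|---|---|
| 45% | 0.45/0.99 = 45.45% (+0.45) | 0.45/0.97 = 46.39% (+1.4) | 0.45/0.95 = 47.37% (+2.4) |
| 30% | 0.30/0.99 = 30.30% (+0.3) | 0.30/0.97 = 30.93% (+0.9) | 0.30/0.95 = 31.58% (+1.6) |

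**Step 4: effect of one death.** Section 2 states "Approximately 160 patients will be randomized in this study global enrollment phase in a 3:1 ratio", which gives 160 × 3/4 = 120 and 160/4 = 40. At a true rate of 45%:

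- arm of 120: 0.45/(1 − 1/120) = 45.38%, about +0.4 point
- arm of 40: 0.45/(1 − 1/40) = 46.15%, +1.15 points

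For scale, the binomial standard error is √(0.45 × 0.55/120) = 4.5 points and √(0.45 × 0.55/40) = 7.9 points.

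**Step 5: simulation check.** There were 3,000 trials per case. The assumptions were exponential PFS with a median of 3 or 5 months, rounded up to 6-weekly scans, follow-up uniform over 9 to 21 months, and early deaths uniform over 0.2 to 1.3 months. Mean 6-month rates for n = 120, deaths as events versus literal rule:

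| Underlying median | q | Deaths as events | Literal rule |
|---|---|---|---|
| 5 months | 1% | 46.0% | 46.5% |
| 5 months | 3% | 45.2% | 46.6% |
| 5 months | 5% | 44.2% | 46.5% |
| 3 months | 5% | 26.5% | 27.9% |

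These agree with the closed form.

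**Step 6: the median.** With 6-weekly scans the median usually stays put. Share of simulated trials in which it moved:

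| Arm size | q = 1% | q = 3% | q = 5% |
|---|---|---|---|
| 120 | 4–5% | 10–14% | 20–24% |
| 40 | 6–9% | 14–21% | 19–32% |

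A smooth exponential curve without scan intervals shows a shift every time: with a 4-month median in the other patients and q = 5%, 4.00 months (literal) against 3.70. The difference comes from ignoring the scan grid, so the simulated result is the better guide.

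**The case against.** The strongest counter-argument is that the SAP has already made the choice. Both the section and the synopsis define death from any cause as an event, and a patient with an observed event is not a candidate for censoring. The paragraph also reads naturally as a rule followed by a fallback: the first sentence needs a last tumor assessment date, and the second supplies a date for a living patient who has no post-baseline one. The OS section is drafted the same way. Section 4.7 describes these rules as handling missing data, and a dated death is not missing.

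This makes the restricted reading the probable intent, and under it no result changes. It does not remove the problem. Section 4.4.1.1 uses nearly the same description, patients lacking any post-baseline tumor assessment, with no stated limit, and there it naturally includes patients who died. A programmer could reasonably read 4.4.2.4 in the same way. The OS parallel does not settle it, for the reason given in step 1 of the working.

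The objection on importance largely stands. The share q is assumed, the shifts lie within sampling error, and Section 2.2.1 says of the ORR comparison with the historical reference: "This is the only comparison with a statistical hypothesis testing". The same deaths remain non-responders for ORR and events for OS.

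**Conclusion.** The concern holds as an ambiguity of wording that gives a wrong result if followed literally. For q of 1% to 5%, the literal reading overstates 6-month PFS by 0.45 to 2.4 points at a true rate of 45%, and by 0.3 to 1.6 points at 30%. Widening the assumptions to q of 2.5% to 10%, with medians of 2.5 to 6 months in the remaining patients, gives about 0.5 to 5.0 points. The upper end requires a tenth of an arm to die unscanned, which nothing in the SAP suggests.

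All these sizes rest on assumed values of q and of the PFS rate or median. The direction does not: unlike sampling error, this bias always lengthens PFS. It touches only a descriptive secondary endpoint. The point is worth correcting but does not threaten the trial's main conclusion.

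**What to change.** Replace the second censoring sentence in Section 4.4.2.4 with wording such as:

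> A patient who is alive without documented progression and has had no tumor assessment after baseline is censored on the randomization date. A patient who dies without any tumor assessment after baseline has a PFS event on the date of death.

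This costs one sentence in the SAP. If the rule was always meant for living patients only, no result changes. Otherwise the PFS estimates may be slightly less favourable than under the literal reading, and they will match the endpoint definition.
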